8.1.3 Laboratory Procedures/Assessments

Details regarding specific laboratory procedures/assessments to be performed in this trial are provided below. The total amount of blood/tissue to be drawn/collected over the course of the trial (from pre-trial to post-trial visits), including approximate blood/tissue volumes drawn/collected by visit and by sample type per subject can be found in the Procedures Manual.

Product: MK-3475

Protocol/Amendment No.: Amendment 5, 21 October 2019

8.1.3.1 Laboratory Safety Evaluations (Hematology, Chemistry and Urinalysis)

Laboratory tests for hematology, chemistry, urinalysis, and others are specified in Table 7. The total amount of blood/tissue to be drawn/collected over the course of the trial (from pre-trial to post-trial visits), including approximate blood/tissue volumes drawn/collected by visit and by sample type per subject can be found in the Procedure Manual.

Laboratory tests for screening should be performed within 10 days prior to the first dose of treatment. If screening laboratory tests occur within this window, they do not have to be repeated on Day 1 of Cycle 1. After Cycle 1, pre-dose laboratory procedures can be conducted up to 72 hours prior to dosing. Results must be reviewed by the Investigator or qualified designee and found to be acceptable prior to each dose of trial treatment.

Remainder of Page Intentionally Left Blank

Product: MK-3475

Protocol/Amendment No.: Amendment 5, 21 October 2019

Table 7: Laboratory Tests

Hematology	Chemistry	Urinalysis	Other-only at specific time points
Hematocrit	Albumin	Blood	Serum β -human chorionic gonadotropin†
Hemoglobin	Alkaline phosphatase	Glucose	(β -hCG)†
Platelet count	Alanine aminotransferase (ALT)	Protein	PT (INR)
WBC (total and differential)	Aspartate aminotransferase (AST)	Specific gravity	aPTT
Red Blood Cell Count		Microscopic exam (If abnormal)	Total triiodothyronine (T3)
Absolute Neutrophil Count	Carbon Dioxide ‡ (CO₂ or bicarbonate)	results are noted	Free tyroxine (T4)
	Calcium	Urine pregnancy test †	Thyroid stimulating hormone (TSH)
	Chloride		Hepatitis Panel
			HA AbIgM, HBsAg HBcAb-IgM, HC Ab
	Glucose		TSH, free T4, prolactin, ACTH, and morning cortisol in case of suspected adrenal insufficiency
	Creatinine		Ketonuria testing in suspected hyperglycemia cases
	Potassium		
	Sodium		Urine for correlative studies
	Total Bilirubin		Blood for correlative studies
	Direct Bilirubin (If total bilirubin is elevated above the upper limit of normal)		
	Total protein		
	Blood Urea Nitrogen		
† Perform on women of childbearing potential only. If urine pregnancy results cannot be confirmed as negative, a serum pregnancy test will be required. ‡ If considered standard of care in your region.			

Product: MK-3475

Protocol/Amendment No.: Amendment 5, 21 October 2019

8.1.3.2 Pharmacokinetic/Pharmacodynamic Evaluations

Serum and whole blood will be collected at screening and at Week 19 for possible pharmacodynamics evaluation. No pharmacokinetic studies are scheduled for this study. [Specimens may be stored until completion of study at local site.](#)

8.1.3.2.1 Blood Collection for Serum MK-3475

Sample collection, storage and shipment instructions for serum samples will be provided in the Procedure Manual. Specimens may be stored until completion of study at local site.

The time points for blood sampling are described in Section 7 – Trial Flow Chart.

8.1.3.2.2 Blood Collection for Anti-MK-3475 Antibodies

Sample collection, storage, and shipment instructions for blood samples will be provided in the Procedure Manual. The time points for blood sampling are described in Section 7 – Trial Flow Chart. Specimens may be stored until completion of study at local site.

8.1.4 Tumor Imaging and Assessment of Disease

Chest X-ray, computerized tomography (CT) urogram or magnetic resonance imaging (MRI) urogram are allowed to ascertain the superficial nature of the disease when indicated according to the standard of care. If urogram protocol not available or contrast allergy/poor renal function preclude such imaging, then non-contrast CT or MRI of the abdomen/pelvis within 90 days of study entry will suffice.

Disease assessment will occur via an evaluation under anesthesia with cystoscopy, cytology, and random bladder biopsies (if indicated for positive findings on cystoscopy or cytology). Assessment will be performed at week 19 (approximately 6 weeks after the last dose of BCG treatment). Assessment will also occur at 3 months, 6 months, 9 months, 12 months, 18 months, and 24 months post treatment visit as per standard of care for the local site. Due to recurrence or maintenance therapy, it is expected that assessments may not fit exactly at these time points. If assessment not completed at that time point, indicate not done on the case report form.

8.1.5 Correlative Studies Specimen Collection

Tumor tissue will be collected at time of clinical biopsy (archival specimen will suffice) at baseline during transurethral bladder resection (if possible) and at Week 19, if a biopsy is clinically indicated. A minimum of 10 paraffin embedded slides are needed for baseline evaluation. Serum, whole blood, and urine will be collected at baseline prior to Day 1, Cycle 1 treatment, Week 4, 7, 8, 9, 10, 11, 12, 13, 16, prior to treatment and at Week 19 prior to cystoscopy. Saliva will be collected at baseline only. Sample collection, storage and shipment instructions for blood and urine samples will be provided in the Procedures Manual. If subjects are followed locally, specimens will be collected if available at 3 month, 6 month, 9 month, 12 month, 18 month, and 24 month post treatment completion visits.

Product: MK-3475

Protocol/Amendment No.: Amendment 5, 21 October 2019

8.1.5.1 Withdrawal/Discontinuation

When a subject discontinues/withdraws prior to trial completion, all applicable activities scheduled for the final trial visit should be performed at the time of discontinuation. Any adverse events which are present at the time of discontinuation/withdrawal should be followed in accordance with the safety requirements outlined in Section 9.0 – Assessing and Recording Adverse Events.

Patients may withdraw from the study at any time for any reason, and without prejudice to further treatment. In addition, patients can be withdrawn by the Investigator because of unacceptable toxicity. Patients who are withdrawn or are removed from the study will be required to have an off-study clinic visit at the time of discontinuation, and a 30-day follow-up safety visit.

Subjects can be withdrawn from the study for any of the following reasons:

Adverse Event: If a subject suffers an adverse event, which in the judgment of the Investigator, the Study Sponsor, or the Data Safety Review Team presents an unacceptable consequence or risk to the subject, the subject can be withdrawn from the study.

Administrative: After consultation, a subject can be withdrawn from the study for the following administrative reasons: 1) failure to complete the protocol-specified evaluations or 2) failure to comply with protocol requirements.

Withdrawal of Informed Consent: A subject can withdraw his consent to participate in the study at his own request or be withdrawn from participation in the study at the request of his legally authorized representative at any time for any reason.

Evidence of Progressive Disease: The Investigator can withdraw a subject from the study if there is a CT scan, MRI or other modality-confirmed progression of disease, but continue to collect follow-up data for safety and overall survival as per protocol.

Subjects **must** be withdrawn/discontinued from the treatment for the following reasons:

- The subject has intercurrent illness that prevents further administration of treatment.
- The subject has a confirmed positive serum pregnancy test.
- The subject is lost to follow-up.

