5.2.4 Schedule Modification for Combination Therapy

The dosing schedule of the combination therapy will not be altered except on an individual drug basis (such as holding either individual BCG or MK-3475 therapy) if the time period is for 2 weeks or less. That is to say holding either of the two medications included in the combination therapy for less than two weeks should not affect the dosage schedule for the other medication. Patients will be discontinued from the trial if one of the two medications is held for more than 2 weeks because of toxicity. BCG treatment may continue, after a 2 week hold, outside of the study at the discretion of the treating Investigator.

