Scheduling Window (Days)	-28 to -1	+/- 3	+/- 3	+/- 1	+/- 1	+/- 1	+/- 1	+/- 1	+/- 1	+/- 3	+/- 3	+/- 3	At time of Discontinuation	30 days Post discontinuation	3,6,9,12,18,24 months Post cyst
Study Treatment															
BCG*				X	X	X	X	X	X						
MK 3475		X	X	X			X			X	X				
Efficacy Measurements															
Cystoscopy ^o	X											X			X
Biopsy (if clinically indicated) ^o	X											X			X
Tumor Biopsies/ Archival Tissue Collection/ Correlative Studies Blood															
Specimen Collection ^p		X ^r	X	X	X	X	X	X	X	X	X	X			X ^p

^aScreening Visit: No study required procedures should be conducted (unless part of routine care) prior to the signing of the informed consent document. Screening Visit laboratory procedures may be used for Day 1 Cycle 1 if completed within 10 days of Day 1 Cycle 1. Restaging imaging of CT urogram or CT/ MRI of abdomen/ pelvis that occurs within 90 days of study entry is acceptable.

^bEarly Discontinuation Visit: All Subjects who discontinue treatment early for any reason should undergo all procedures listed in the Flow Chart for Discontinuation Visit.

^cIf a subject has completed all study treatment, the subject should complete the 30 day Safety Follow-Up Visit procedures listed in the Flow Chart.

^dFollow-Up Visits should occur at approximately 3, 6, 9, 12, 18, and 24 months from Week 19 cystoscopy. It is expected that follow up data will be collected from routine office visits which generally occur every three months in this population. There may be a shift in schedules if the participant has been given maintenance therapy or was found to have a recurrence. Subject will complete final set

Product: MK-3475

Protocol/Amendment No.: Amendment 5, 21 October 2019

of Questionnaires at the 3 month visit. Follow-Up information may be collected via medical record and document review only. However, patient contact via phone or in person may occur if information is not available via chart review.

^eSubject Identification card may be given at any time after consent process has occurred and prior to treatment on Day 1 Cycle 1.

^fPrior and concomitant medications will include any medications taken within the 28 days prior to consent and through the safety visit and will include prescribed, over-the counter and herbal/alternative remedies.

^gPost-study treatment anti-cancer therapy and recurrence status may be collected through follow-up chart review.

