8.1.6.5 Treatment Discontinuation/Safety Follow-Up Visit

The Treatment Discontinuation Visit and Safety Follow-Up Visit include identical procedures and assessments. Subjects withdrawn from treatment prior to completion of the Treatment Period should undergo a Discontinuation Visit for safety purposes and may occur any time within 30 days of the subject discontinuing treatment, but preferably prior to the subject initiating a new treatment. The mandatory Safety Follow-Up Visit should be conducted approximately 30 days after the last dose of trial treatment or before the initiation of a new anti-cancer treatment, whichever comes first. All AEs that occur prior to the Safety Follow-Up Visit should be recorded. Subjects with an AE of Grade >1 will be followed until the resolution of the AE to Grade 0-1 or until the beginning of a new anti-neoplastic therapy,

Product: MK-3475

Protocol/Amendment No.: Amendment 5, 21 October 2019

whichever occurs first. SAEs that occur within 30 days of the end of treatment or before initiation of a new anti-cancer treatment should also be followed and recorded.

Assessments at the Discontinuation/Safety Follow-Up Visit include a full physical examination, ECOG Performance Status and vital signs. Laboratory assessments include hematology, chemistry, and urinalysis, as well as evaluation of thyroid function. Concomitant medications and toxicity assessment will be recorded as well.

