8.1.6.6 Follow-up Visits

Subjects who complete all study treatment or discontinue trial treatment for a reason other than disease progression will move into the Follow-Up Phase and should be assessed at 19 week cystoscopy. Additional follow up information will be collected at 3, 6, 9, 12, 18, and 24 months post completion of treatment. Every effort should be made to collect information regarding disease status, start of new anti-neoplastic therapy, disease recurrence, disease progression, death, or end of the study. Information regarding post-study anti-neoplastic treatment will be collected if new treatment is initiated.

A final set of AUA IPSS and QOL questionnaires are also to be administered at the 3 month Follow Up visit.

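### The protocol conflicts with itself on whether a subject who stops treatment early is still assessed for response, and on the date from which the 3 to 24 month visits are counted

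*Combined protocol and SAP*

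**What the plan says.** **Whether a stopper is assessed.** Section 5.2.4: "Patients will be discontinued from the trial if one of the two medications is held for more than 2 weeks because of toxicity". For subjects leaving the study, section 8.1.5.1 adds: "Patients who are withdrawn or are removed from the study will be required to have an off-study clinic visit at the time of discontinuation", and requires a 30-day safety visit. Footnote b to the flow chart in 7.1 reads: "All Subjects who discontinue treatment early for any reason should undergo all procedures listed in the Flow Chart for Discontinuation Visit". In that chart, cystoscopy and biopsy are marked at screening, Week 19 and follow-up only. Section 8.1.6.5 describes the visit in safety terms: "Assessments at the Discontinuation/Safety Follow-Up Visit include a full physical examination, ECOG Performance Status and vital signs", plus laboratory tests, concomitant medication and toxicity.

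Section 8.1.6.6 gives a different route. Subjects who complete treatment, or who "discontinue trial treatment for a reason other than disease progression will move into the Follow-Up Phase and should be assessed at 19 week cystoscopy", stay under observation.

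Sections 5.2.1.1.3 and 5.3.2 add discretion. After a steroid-related BCG delay of more than two weeks, the investigator chooses between ending BCG within the study and withdrawing the subject from the study.

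**From when follow-up is counted.** Footnote d in 7.1 counts the 3 to 24 month visits from the Week 19 cystoscopy, and the chart's column header agrees. Section 8.1.6.6 says: "Additional follow up information will be collected at 3, 6, 9, 12, 18, and 24 months post completion of treatment". Sections 8.1.5 and 10.1 also count from completion of treatment. Sections 3.2, 4.2.3.1 and 8.1.4 refer only to post-treatment visits.

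**The concern.** Complete response at Week 19 and at 3, 12 and 24 months is the only secondary objective (3.2). A site handling a toxicity stopper can follow 5.2.4 and 8.1.5.1 and end with two safety visits, or follow 8.1.6.6 and obtain the Week 19 cystoscopy. Both are defensible readings, so whether the outcome exists may depend on which section the site reads.

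The second conflict concerns comparability. If the clock starts at each subject's own last dose, a 3-month response in an early stopper is observed after less elapsed time than a 3-month response in a completer, yet both enter one proportion.

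Section 8.1.4 says only that a missed assessment is recorded as not done. Section 10.1 gives no rule for counting it.

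**Working it through.** The plan gives no figure to reproduce here: response is descriptive, with no power or error rate attached. The check is calendar arithmetic and a simple proportion.

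**Inputs.** MK-3475 is marked at Weeks 1, 4, 7, 10, 13 and 16 (7.1), in 21-day cycles. The disease assessment is at Week 19. There are 15 subjects (10.1). One month is 365.25 / 12 / 7 = 4.348 weeks, so 3 months is 13.0 weeks.

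**Formulas.** For a last MK-3475 dose at week w, the 3-month visit falls at:
- w + 13 if counted from the last dose;
- w + 3 + 13 if counted from the end of the last cycle;
- 19 + 13 = 32 if counted from the Week 19 cystoscopy.

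| Last dose (week) | From last dose | From end of last cycle | From Week 19 | Weeks earlier than a completer, under either of the subject's own origins |
|---|---|---|---|---|
| 1 | 14 | 17 | 32 | 15 |
| 4 | 17 | 20 | 32 | 12 |
| 7 | 20 | 23 | 32 | 9 |
| 10 | 23 | 26 | 32 | 6 |
| 13 | 26 | 29 | 32 | 3 |
| 16 (completer) | 29 | 32 | 32 | 0 |

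Counted from the last dose, a stop at Week 1 or 4 puts the 3-month visit (Week 14 or 17) before the Week 19 assessment. Counted from the end of the last cycle, this happens only for a stop at Week 1. The lag of 3 to 15 weeks is the same at 12 and 24 months.

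With the Week 19 origin for everyone, the 3, 12 and 24 month visits fall at about Weeks 32, 71 (19 + 52.2) and 123 (19 + 104.4), and the lag is zero.

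**Weight of one lost outcome.** 1/15 = 6.7 percentage points.

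**Illustration (assumed counts, not in the documents).** Suppose 3 of 15 stop unassessed and 6 of the other 12 respond:
- stoppers dropped: 6/12 = 50%;
- stoppers counted as non-responders: 6/15 = 40%;
- stoppers all responders: 9/15 = 60%.

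The first two results differ only by choice of denominator. The range from 40% to 60% is what remains unknown without an assessment.

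**The case against.** The strongest reply is that a harmonious reading exists. Section 8.1.5.1 concerns leaving the study and 8.1.6.6 concerns leaving treatment. Taking 8.1.6.6 together with footnote d, every non-progressing stopper has the Week 19 cystoscopy and visits counted from it, and neither problem arises. That reading is available, but the protocol does not direct sites to it, and 5.2.4 blurs the distinction by removing toxicity stoppers from the trial itself.

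Section 8.1.5.1 also opens with this instruction: "all applicable activities scheduled for the final trial visit should be performed at the time of discontinuation". If the final visit is a follow-up visit, that would bring in a cystoscopy. The Discontinuation column shows none, however, and an assessment on the day of stopping is not a Week 19 assessment. Recurrence status is marked at Discontinuation, and footnote g lets it come from chart review, so some information may be captured without a procedure.

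Four stronger readings might be inferred, and the documents do not support them:
- **That progressors are lost.** A subject stopped for documented progression is already a known non-responder. Section 8.1.5.1 tells investigators to "continue to collect follow-up data for safety and overall survival as per protocol", which can coexist with exclusion from the cystoscopy schedule in 8.1.6.6. Section 8.1.1.6.3 keeps subjects on new anti-cancer therapy in survival follow-up.
- **That the timing gaps are certain.** No section defines completion of treatment as the subject's own last dose. Section 8.1.6.2.1 equates the end of therapy with Week 19; on that reading the two origins agree.
- **That the response rates are biased upward.** This requires that stoppers respond less often and that unassessed subjects are dropped. Neither is stated, and 5.7 declares an intent-to-treat population.
- **That no analysis rule could help.** Counting unassessed subjects as non-responders fixes the denominator. It does not recover their true status or align the assessment times.

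**Conclusion.** The conflict is real and in the current text. Sections 5.2.4, 7.1 (footnote b), 8.1.5.1 and 8.1.6.5 lead a toxicity stopper to visits without cystoscopy, while 8.1.6.6 leads a treatment stopper to the Week 19 cystoscopy. The follow-up origin is stated in two ways.

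The timing effect is conditional. It is 3 to 15 weeks if completion means the subject's own last MK-3475 dose or the end of that cycle, and nil if it means Week 19. Loss of outcomes is also conditional on which section a site follows. Each lost outcome is worth about 7 percentage points among 15 subjects. Upward bias is the likely direction if unassessed stoppers are left out, but it is not demonstrated.

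Response is a secondary, descriptive endpoint, so no error rate is affected. The point deserves correction because the ambiguity affects what is collected, and an outcome that was never assessed or recorded cannot be supplied at analysis.

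**What to change.** Leave the treatment-stopping rules and the grounds for withdrawal as they are; this point takes no position on them. Then make three changes.

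1. **Outcome collection.** Reconcile 5.2.4, 5.2.1.1.3, 5.3.2, 8.1.5.1 and 8.1.6.6 by stating that stopping trial treatment, for any reason, does not by itself end outcome collection. Every treated subject who has not withdrawn consent, died or been lost to follow-up keeps the Week 19 disease assessment, or its standard-of-care equivalent by chart review, and the follow-up visits. Documented recurrence, progression or cystectomy counts as non-response.
2. **One origin.** In 7.1, 8.1.4, 8.1.5, 8.1.6.6 and 10.1, count the 3 to 24 month visits from the Week 19 assessment. If that was not done, count from the Week 19 date reckoned from Day 1 of Cycle 1.
3. **Reporting.** In 10.1, report complete response over all treated subjects at each time point and show the number unassessed.

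The cost is mostly wording. Footnotes d, g and o in 7.1 already provide for chart review and standard-of-care cystoscopy. The downside is retrieving records for a few stoppers, and possibly a slightly less favourable response rate.

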8.1.6 Visit Requirements

Visit requirements are outlined in Section 7.0 – Trial Flow Chart. Specific procedure-related details are provided above in Section 8.1 – Trial Procedures.

Product: MK-3475

Protocol/Amendment No.: Amendment 5, 21 October 2019

8.1.6.1 Screening

8.1.6.1.1 Screening Period

The screening period covers the 90 days prior to Day 1, Cycle 1. Days –90 through –28 will include restaging for Ta and T1 tumors.

The study screening visit is mandatory and must occur in the 28 days prior to Day 1, Cycle 1 of treatment. The study screening visit includes full study informed consent and documentation of consent. No study required procedures (excluding those that are standard of care) are to occur prior to informed consent of the subject. All inclusion/exclusion criteria must be reviewed and all of the inclusion and none of the exclusion criteria must be met to advance the subject on to the Treatment Period. The screening period procedures include: full study informed consent, review of inclusion/exclusion criteria, documentation of demographics and medical history, concomitant medication review, cystoscopy and urine cytology, including restaging of tumor for Ta and T1, review of ongoing symptoms for documentation of baseline adverse effects, full physical examination, ECOG performance status, vital signs, electrocardiogram, chest X-ray, and baseline pulmonary function tests as well as laboratory assessments indicated in Section 7–Trial Flow Chart. Collection of a baseline bladder cancer tumor specimen, as well as baseline blood and urine specimens for correlative studies, will also occur during the screening period. Assessment of coagulation status will be performed prior to each resection as per standard of care.

